4.3. Residual risks associated with PA1704

At this stage in the verification and validation of the design of the PA1704 device, all the identified risks associated with the manufacture and use of the medical device in the intended indication have been taken into account. In order to minimize or eliminate these risks, contraindications, warnings and precautions for use have been reported in chapter 2 and the Investigator's Brochure.

There is no unacceptable residual risk associated with PA1704.

4.4. Risks associated with taking part in clinical trials.

In this clinical trial, with the exception of the MD under investigation PA1704, all examinations, surgical procedures and products used (including the comparator MD) are the same as those used in current practice.

The risks are the same as in current practice, i.e. those associated with anesthesia and mechanical treatment procedures, disinfection and obturation of the canal:

- Risks associated with the anesthetic protocol: reactions associated with high plasma uptake of the
 anesthetic (e.g. in the event of inflammation at the injection site or accidental intravascular
 administration: tremors, dizziness, malaise), local reactions at the injection site.
- Risks associated with mechanical root canal treatment: over— or under-filling, fracture of an
 instrument in the canal, ingestion of an instrument, post-operative pain, fracture or cracking of a
 root.
- Risks associated with root canal disinfection: ingestion of disinfectant (usually hypochlorite), allergy, irritation.
- As far as the root canal filling stage is concerned, the possible risks are under— and over-filling. These
 clinical situations can lead to post-operative pain that is not related to the cement itself, but to reinfection and tissue necrosis, on the one hand, and ligament and nerve tissue compress on the other.
 Compression of the periapical tissues can lead to paresthesia or hypoesthesia. In most cases, repeat
 endodontic treatment is necessary in the event of under-filling.

4.5. Possible interactions with concomitant medical treatments.

None.

4.6. Steps taken to control or mitigate risks.

See Chapter 2.11 entitled "Warnings".

4.7. Rationale for the benefit-risk ratio.

The clinical trial does not entail any benefit for the people who take part in the trial, but does not present any significant risk or constraint.

5. Objectives and hypotheses of the clinical trial

5.1. Primary and secondary objectives.

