5.2. Hypothesis to be accepted or rejected on the basis of statistical data from the clinical trial.

The OPTIFILL clinical trial is a non-inferiority trial; the aim is to show that the 2-year efficacy rates for the 2 filling materials PA1704 and BioRoot™ RCS are comparable.

i.e.:

 π_N = 2-year efficacy rate of PA1704 based on soft radiological and clinical criteria,

π_R = 2-year efficacy rate of BioRoot™ RCS based on soft radiological and clinical criteria,

 $\Delta = \pi_N - \pi_R$, the difference in efficacy at 2 years between the 2 treatments,

 Δ_L = limit corresponding to a clinically insignificant difference (i.e. the greatest difference in tolerated efficacy between the 2 products) (see Chapter 7.2 for details).

The hypotheses are:

H0: $\Delta \le -\Delta_L$, PA1704 is inferior to BioRoot[™] RCS

H1: $\Delta > -\Delta_L$, non-inferiority of PA1704 compared to BioRoot[™] RCS

Using Dunnett and Gent's χ^2 test (Dunnett CW and Gent M. 1977; Elie C. et al., 2008), we will reject H0 and conclude that the new PA1704 material is not inferior to the BioRootTM RCS reference material if the difference in efficacy between the 2 products is greater than the non-inferiority limit (see Figure 3).

[figure not shown]

Figure 3: Non-inferiority trial and associated hypotheses (according to Elie et al., 2008).

5.3. Claims and expected performance of the device under investigation that need to be verified.

- Permanent filling of the root canals of permanent and mature teeth.
- Preservation of tooth function.

5.4. Risks and undesirable effects expected from the device, which must be assessed.

The adverse effects of the device are not known in the patient and will be investigated, in particular the occurrence of any allergic reaction, as soon as the material is applied to the root canals.

6. Clinical trial design

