If the patient is seen for treatment outside the protocol (routine care) or for any emergency, the investigator shall collect all the information relevant to the trial (date of consultation, reason for consultation, occurrence of AEs, etc.).

V3 — Clinical follow-up visit at 6 months (± 1 month) — Standard practice

- **Clinical examination**: Verification of the functional status of the treated tooth and percussion test (lateral and axial),
- Recording of AEs.
- Retro-alveolar X-ray check to evaluate the results of endodontic treatment at 6 months: 1) density of the root canal filling (radiopacity + presence of voids), 2) progress of resorption of the extruded material

where appropriate, **3)** apical lesion (absence/appearance/still present compared with T0) and progress of the size of an existing lesion (reduction, stabilization or increase).

Upload the 6-month follow-up retro-alveolar image to the eCRF (reminder: the entire tooth – from the *crown to the apex, including the root* – must be visible in the image; see chapter 6.1).

— The investigator shall evaluate the efficacy of the endodontic treatment on the basis of the clinical and radiological criteria identified (*Note: Only the evaluation of the radiological criteria by the independent reviewers will be taken into account for the primary evaluation criterion (PEC); the investigator's evaluation is to be used to determine further clinical follow-up*).

Procedure in the event of the appearance of a lesion or an increase in the size of a pre-existing lesion:

- If the investigator considers it to be an emergency (e.g. if the tooth is symptomatic and/or non-functional): the investigator will notify the patient of the failure of the endodontic treatment and schedule retreatment. In this case, the patient leaves the trial early due to the failure of the treatment and continues endodontic treatment outside the trial (end-of-trial form to be completed in the eCRF). Performance and safety evaluations now end. Failure notified at 6 months is carried forward as the PEC value (response at 24 months = failure). The patient will not be replaced.
- If the investigator considers that it is NOT an emergency (e.g. if the tooth is asymptomatic): medical advice should be sought from the trial coordinator (who will review the X-rays) before considering retreatment and early discharge from the trial for treatment failure.

V4 — Clinical follow-up visit at 12 months (± 1 month) — Standard practice

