6.6.5. Data quality & monitoring

Data monitoring will be carried out by the CRO's CRAs, in accordance with Good Clinical Practice aimed at guaranteeing the quality of the trial. As the OPTIFILL trial is a category 1 RIPH involving a class IIa medical device that is not CE marked, the level of control will be high.

The CRAs will carry out regular remote monitoring *via* the ENNOV Clinical software application to track recruitment and check the integrity of the data entered into the eCRF. Requests for corrections or clarification of data will be sent to the investigator electronically.

In addition, the CRO's CRAs will regularly visit the investigating centres; 6 site visits are planned: 1 visit soon after the first enrolments, then a site visit after each follow-up visit provided for in the protocol, for up to 5 years of patient follow-up. The CRAs will check and verify consent forms, the consistency of critical data (PEC clinical criteria, AEs, patient record data, device defects) and equipment.

Visits will be organized after making an appointment with the investigator. The CRA must be able to consult:

- Consent forms,
- Observation and monitoring records,
- Patient source files (paper and/or electronic format),
- Medical devices made available (PA1704 and Bioroot™ RCS)
- Investigator file provided by the CRO.

7. Statistical considerations

7.1. Software used:

 Creation of the input template for the electronic CRF and patient record, database media: Ennov Clinical version 8.0,

Statistical analysis: JMP[®] version 15.0.0 or later (SAS Institute) on Windows 10 Pro.

7.2. Size of sample:

Based on the assumption that there is no difference in efficacy at 2 years between the 2 filling materials (PA1704 and BioRoot™ RCS) and that the expected efficacy rate of BioRoot™ RCS after initial and repeated endodontic treatment is 90% (Zavattini et al., 2019; Chybowski et al., 2018, Bardini et al., 2016), we calculate that a minimum of 66 subjects per group must be enrolled **to show non-inferiority of PA1704 over BioRoot™ RCS** with a confidence interval of 80%, a unilateral alpha risk of 5% and a 13% difference in efficacy tolerance between the 2 products (Ng 2007; Ng 2008; Eyuboglu 2016). By enrolling an additional 20% of patients in order to take into account those lost to or withdrawn from the trial, **the number of patients who must be included is 80 in each group, or 160 patients in total.**

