7.3. Degree of significance and power of the clinical trial

The main analysis will be carried out using a one-tailed statistical test with a significance threshold α set at 5%. The clinical trial is designed to ensure 80% power for the main analysis test. Secondary analyses will be carried out using two-tailed statistical tests with a significance threshold α set at 5%.

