The Per Protocol (PP) population is the entire mITT population that perfectly complied with the protocol. Thus, subjects with major protocol violations, including major false inclusions (see below), and subjects for whom the primary criterion was not available, will be excluded from the PP population.

Major enrolment breaches include:

- No signed consent,
- Enrolment of a vulnerable subject,
- Enrolment of a patient with a contraindication to endodontic treatment or a known contraindication to the use of BioRoot™ RCS or PA1704 filling material,

Major deviations from the protocol include:

- Error in allocating the medical device,
- Failure to comply with the procedure for using the medical device,
- · Coronal restoration procedure contraindicated or insufficient,
- · Lost contact,
- No performance data,

Particular care will be taken to describe any deviations from the protocol.

All major deviations will be validated by the coordinating investigator, ideally during clinical implementation and monitoring visits, or at the latest at the time of data review; the evaluation will be carried out blind to the data relating to whichever medical device was allocated and data collected after randomization.

It should be noted that non-compliance with the schedule of visits scheduled at 6, 12 and 24 months (with a tolerance of \pm 1 month) will be considered a minor deviation from the protocol; the same applies in the case of a coronal restoration carried out after more than 45 days.

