 - o Preoperative pain (symptomatic tooth at enrolment, preoperative VAS).

7.7.11. Handling missing, unused or erroneous data, including drop-outs and withdrawals:

No imputation method is planned. However, as stated above, patients with treatment failure at 6 or 12 months will be withdrawn from the study and will be considered to have treatment failure at 24 months.

7.7.12. Exclusion of certain information from the hypothesis tests, if relevant:

None.

7.7.13. In the case of multi-center investigations, minimum and maximum number of subjects to be included for each center:

Each center will include 22 to 24 patients with an indication for initial or repeat endodontic treatment. The number of repeat treatments may vary between centers, but will total 30% in the sample. Some investigators, because of their specialty in endodontics, will include a majority of patients with an indication for repeat treatment, whereas GP investigators will probably have more indications for first-line treatment.

8. Data management

Procedures for examining data, cleaning databases, issuing and resolving data queries:

See Chapter 6.6, Data quality and monitoring section.

Procedures for verification, validation and securing of the electronic clinical data systems, where applicable:

The data collected in electronic CRFs is recorded directly in an electronic database using ENNOV software and hosted on a secure health data server in accordance with current regulations. The data collected in the paper logbooks is entered by the CRO into the electronic database using ENNOV software.

Data retention:

See the Archiving section in Chapter 12.4.

9. Amendments to the clinical investigation plan

Requests for substantial modifications will be sent by the CRO, on behalf of the sponsor, to the relevant ethics committees for their opinion and to the competent authorities for authorization, in accordance with law 2004-806 of 9 August 2004 and its implementing decrees in force.

Similarly, non-substantial modifications will be sent for information.

An updated version of the amended protocol must be dated. This new version will be sent to the investigators.

The patient information leaflet should be amended if necessary.

10. Deviations from the clinical investigation plan

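### Loss of the study tooth has no outcome class: unless failure was recorded at 6 or 12 months, an extracted tooth has no 24-month value and, read literally, leaves the primary analysis

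*Combined protocol and SAP*

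**What the plan says.** The primary criterion (6.1, 7.7.4) joins a blinded reading of the apical lesion with the investigator's finding on function and pain. Table 4 maps these to effective, uncertain or ineffective treatment. All of its rows need a follow-up radiograph of the treated tooth, and none covers a tooth that is no longer there.

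Four other rules bear on such a patient:

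- **Populations (7.6).** "subjects for whom the primary criterion was not available, will be excluded from the PP population". The mITT set needs at least one efficacy assessment at 6, 12 or 24 months. Section 7.7.4 makes PP the main analysis and mITT the supportive one.
- **Missing data (7.7.11).** "No imputation method is planned".
- **Carry-forward (6.5.2, 7.7.4, 7.7.11).** A failure at 6 or 12 months counts as a failure at 24 months.
- **Visit instructions (6.5.2, V3 and V4).** The failure procedure is headed "Procedure in the event of the appearance of a lesion or an increase in the size of a pre-existing lesion" and leads to retreatment. At V5, failure is notified on the same lesion trigger.

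The withdrawal criteria in 6.3 mention failure that needs repeat treatment. They do not mention extraction. Section 4.4 lists "post-operative pain, fracture or cracking of a" root among the procedural risks, and 5.3 names "Preservation of tooth function" as a performance claim to be verified.

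**The concern.** A patient whose study tooth has been extracted can attend every visit and have a fully known, unfavourable result. There is no apex to image, so Table 4 returns nothing. The value is absent because the endpoint definition has no place for it, not because anyone failed to observe it.

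Read literally, 7.6 then removes the patient from PP. If the tooth is lost after an earlier assessment, mITT keeps the patient without a 24-month value. If it is lost before the 6-month assessment, the patient may not enter mITT at all. The supportive analysis therefore has the same gap and cannot reveal the problem.

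Efficacy would then be estimated among retained teeth only, in a trial whose stated claim includes keeping a functioning tooth. Whether this shifts the non-inferiority comparison depends on whether tooth loss differs between the arms.

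**Working it through.** **1. The plan's own sample size.** Section 7.2 gives "a unilateral alpha risk of 5% and a 13% difference in efficacy tolerance between the 2 products" and states that "the expected efficacy rate of BioRoot™ RCS after initial and repeated endodontic treatment is 90"%, with no true difference. Section 7.3 adds: "The clinical trial is designed to ensure 80% power for the main analysis test". With unpooled variance:

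n = [0.9×0.1 + 0.9×0.1] × (1.645 + 0.842)² / 0.13² = 65.85, rounded up to 66 per arm.

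This reproduces the stated figure. Power at 66 per arm is 80.1%. If 90% is read as the rate with tooth loss already counted as failure, 66 is unchanged by the fix.

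**2. False non-inferiority when lost teeth are left out.** The documents give no extraction rate, so the rates below are assumptions. They refer to teeth lost without an earlier recorded failure. Set true efficacy, with lost teeth counted as failures, at the margin: 90% for BioRoot RCS (C) and 77% for PA1704 (T). With loss proportions eC and eT, the rates among retained teeth are

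pC = 0.90/(1−eC), pT = 0.77/(1−eT), with nC = 66(1−eC), nT = 66(1−eT).

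P(declare non-inferiority) = Φ[(pT − pC + 0.13)/SE − 1.645], SE = √[pC(1−pC)/nC + pT(1−pT)/nT].

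| Lost, BioRoot / PA1704 | pC | pT | Apparent difference | False non-inferiority |
|---|---|---|---|---|
| counted as failures | 0.9000 | 0.7700 | −0.1300 | 5.0% |
| 1% / 1% | 0.9091 | 0.7778 | −0.1313 | 4.8% |
| 2% / 2% | 0.9184 | 0.7857 | −0.1327 | 4.6% |
| 5% / 5% | 0.9474 | 0.8105 | −0.1368 | 3.9% |
| 1% / 3% | 0.9091 | 0.7938 | −0.1153 | 8.0% |
| 2% / 5% | 0.9184 | 0.8105 | −0.1078 | 10.1% |
| 2% / 7% | 0.9184 | 0.8280 | −0.0904 | 16.5% |
| 2% / 10% | 0.9184 | 0.8556 | −0.0628 | 32.1% |

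Differences are from unrounded rates. Equal loss makes the plan slightly conservative. Greater loss with PA1704 makes it anti-conservative, and greater loss with BioRoot RCS would work against PA1704.

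**3. How few teeth matter.** Take 66 per arm and six failures per arm among retained teeth. The one-sided 95% lower limit is d − 1.645×SE (Wald), in percentage points:

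| Lost, BioRoot v PA1704 | Excluded | Limit | Counted as failures | Limit |
|---|---|---|---|---|
| 1 v 1 | 59/65 v 59/65 | −8.35 | 59/66 v 59/66 | −8.82 |
| 1 v 3 | 59/65 v 57/63 | −8.77 | 59/66 v 57/66 | −12.37 |
| 1 v 4 | 59/65 v 56/62 | −8.99 | 59/66 v 56/66 | −14.11 |

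At 1 v 3 the conclusion is the same either way. At 1 v 4 it reverses: non-inferior if the teeth are excluded, not shown if they are counted. Section 7.7.4 does not name its interval method, so these limits are approximations to the planned analysis.

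**The case against.** **Carry-forward already protects the analysis.** In part it does. A reader might infer that every extracted tooth disappears from the primary analysis, but the documents do not support that. Once failure is recorded at 6 or 12 months, later extraction changes nothing and the patient remains a failure. Nor is a new or growing lesion the only route to failure: Table 4 also classes a stable lesion as ineffective when the tooth is symptomatic or not functional. What remains is a tooth lost with no failure recorded at either visit, for example between visits or between 12 and 24 months.

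**An extracted tooth is plainly non-functional, so it would be counted as failed.** Table 4 does not work that way. A shrinking lesion in a tooth that is both symptomatic and non-functional is classed as uncertain, and the main soft analysis in 6.1 groups uncertain with effective treatment. A lesion-free but non-functional tooth has no row at all. Loss of function alone does not decide the class.

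**Exclusion is inferred from silence.** This stands. No sentence says that extracted teeth are excluded. Section 7.7 leaves detail to a separate Statistical Analysis Plan, which is not part of the document reviewed and may settle the matter. The data review in 7.5 is a weaker safeguard, because 7.6 requires major deviations to be judged blind to data collected after randomisation, and tooth loss is such data.

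**Nothing suggests that loss would differ by sealer.** This also stands. Section 4.4 places root fracture under mechanical canal treatment, which is common to both arms and precedes the sealer, and does not say that it leads to extraction.

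**Conclusion.** The gap is real and narrower than it may first appear. A tooth lost before the 24-month visit, with no failure recorded at 6 or 12 months, has no Table 4 result. Taken literally, 7.6, 7.7.4 and 7.7.11 then drop a known bad outcome from PP and leave no 24-month value in mITT.

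A reader might go further and infer that the plan is biased in favour of PA1704. The documents do not support that: they give neither an extraction rate nor an arm difference, and with equal loss the error rate falls slightly. The 8-32% range holds only if PA1704 loses more teeth, at the assumed rates and under the normal approximation. What can be said is that a difference of three lost teeth (1 v 4) can decide the result in the example above, and that the plan does not fix how they are handled. Investigators know the allocation, so the rule should be settled before outcome data are examined.

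**What to change.** Add one outcome class to Table 4 and repeat it in 7.6 and 7.7.4, along these lines:

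> Loss or extraction of the study tooth at any time up to the 24-month visit is classed as ineffective treatment at 24 months. The primary criterion counts as available for that patient.

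It should stand as its own rule and not be derived from non-functionality, because Table 4 does not treat a non-functional tooth as ineffective in every row. Record the date of and reason for each loss in the eCRF.

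Add one sensitivity analysis that leaves out extractions judged, blind to arm, to be unrelated to the endodontic treatment. Counting loss from any cause is a choice about what the trial estimates, and this analysis shows whether the choice matters.

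The cost is one table row, a sentence in each of two sections, eCRF fields for date and reason, and one extra analysis. The planned 66 per arm stays if 90% is understood to include tooth loss. The downside is small: a few unrelated extractions will count as failures in both arms.

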7.7. Statistical methods

The statistical methods are based on the following elements and will be detailed in the Statistical Analysis Plan.

7.7.1. Sample description:

The description of the subjects enrolled who completed the trial and those enrolled who left prematurely will be presented using a table of absolute (N) and relative (%) frequency. Reasons for premature discharge and deviations from the protocol will be listed.

7.7.2. Descriptive analyses:

Clinical data collected at enrolment and at each visit will be described. Descriptive statistics will be presented according to the nature of the criterion analyzed:

- Quantitative variable: sample size, number of missing data sets, mean, standard deviation, median, minimum and maximum;
- Qualitative variable: absolute frequencies (N) and relative frequencies (%) per class in each group, number of missing data.

Graphs will be provided for each variable.

7.7.3. Comparative analyses:

A comparison of 2 independent means will be made using the Student's t-test; if the variances are unequal (verified by the Fisher's test), use the Welch's test instead of the Student's test. If the conditions for applying the Student test are not met (n < 30), the non-parametric Wilcoxon test is used.

2 independent percentages are compared using Pearson's Chi-2 test. If the conditions for application are not met (at least one theoretical number < 5), Fisher's exact test is used.

7.7.4. Analysis of primary performance criterion:

As a reminder, the primary performance criterion is the efficacy rate at 24 months of treatment based on clinical criteria assessed by the investigator (tooth functionality and pain level) AND radiological criteria assessed blind by independent reviewers (complete healing, reduction of lesions, failure). In the event of failure at 6 or 12 months, the patient will be considered to have failed at 24 months.

The primary criterion will be analyzed using 2 approaches, in accordance with the literature:

- **Primary analysis of soft criteria**: treatment rates with complete or incomplete cure are compared against failure rates;
- **Secondary analysis of strict criteria**: treatment rates with complete healing are compared against rates of failure or incomplete healing (complete healing can take up to 4 or 5 years).

The comparison of efficacy rates between the 2 groups will be carried out using the Dunnett and Gent χ^2 test (Dunnett CW and Gent M 1977; Elie C et al 2008).

In addition, the difference in the 2-year efficacy rate between the 2 materials are to be calculated; its unilateral confidence interval of 95% will be provided and the lower limit is will be compared against the non-inferiority limit.

The main performance analysis will be carried out on the PP population, in accordance with the recommendations for non-inferiority studies. This will be complemented by an analysis of the mITT population to check the stability of the results.

7.7.5. Analysis of secondary performance criteria:

Efficacy rate at 6 months based on radiological and clinical criteria: Description and comparison, between the PA1704 arm and the BioRoot™ RCS arm, of the 6-month efficacy rate by Pearson's Chi-2 test or Fisher's exact test.

Efficacy rate at 12 months based on radiological and clinical criteria: Description and comparison, between the PA1704 arm and the BioRoot™ RCS arm, of the 12-month efficacy rate by Pearson's Chi-2 test or Fisher's exact test.

Quality of apical obturation at T0 (complete obturation, under-filling or over-filling): Description and comparison, between the PA1704 arm and the BioRoot™ RCS arm, of the proportions of apical obturation quality by Pearson's Chi-2 test or Fisher's exact test.

Density of root canal filling at T0, 6 months, 12 months, 24 months: Description and comparison at each time point, between the PA1704 arm and the BioRoot™ RCS arm, of the proportions of canals with an

obturation density deemed sufficient and the proportions of canals free of voids, by Pearson's Chi-2 tests or Fisher's exact tests.

Progress of material resorption over 24 months, in the event of over-filling at T0 (6 months, 12 months and 24 months): Description and comparison, between the PA1704 arm and the BioRoot™ RCS arm, of the proportions of patients with resorbed materials among patients who were over-filled at T0 by Pearson's Chi-2 test or Fisher's exact test.

Pre-operative and post-operative pain experienced by the patient (VAS 0-100 mm) at T0 (end of surgery), 12h, 24h, 48h, 72h and 7 days: For each time point, description and comparison of the pain, between the PA1704 arm and the BioRoot™ RCS arm, by a Student, Welch or Wilcoxon test. A figure representing average pain as a function of assessment times per arm will be provided. The causes of the pain will be described.

Maximum pain in the first 7 days and time to onset of maximum pain: Description and comparison, between the PA1704 arm and the BioRoot™ RCS arm, of the maximum pain experienced during the 7 post-operative days and its time to onset by a Student, Welch or Wilcoxon test.

Intra-operative pain relief between T0 and D7: Description of painkiller classes, reasons for use, frequency of use and cumulative dose per patient over 7 days. Description and comparison, between the PA1704 arm and the BioRoot™ RCS arm, of the proportion of patients who used *oral* pain medication between T0 and D7 by Pearson's Chi-2 test or Fisher's exact test.

Description of the surgical technique: Description and comparison, between the PA1704 arm and the BioRoot™ RCS arm, of the type of anesthesia, the technique used to remove the old filling material (if root canal re-treatment only), the technique used to shape the canal, the type of disinfectant and rinse solutions used and irrigation techniques, the method of application of filling material and gutta-percha condensation, and the coronal restoration technique, by Pearson's Chi-squared test or Fisher's exact test. Intraoperative complications will be described where appropriate.

Operator comfort and satisfaction: Description and comparison, between the PA1704 arm and the BioRoot™ RCS arm, of operator comfort criteria. Satisfaction will be described at T0 and 2 years, and the proportions of satisfied operators will be compared.

For the performance criteria (efficacy rate, filling density, and material resorption) evaluated at 3.5 years and 5 years in the PA1704 arm: These criteria will only be described.

7.7.6. Safety/tolerance analysis:

The tolerance analysis will focus on the Tolerance population. Tolerance data is to be expressed as the number of adverse events (AEs) and the number of patients reporting at least one AE. Severity, cause (filling material or surgical technique) and the time of occurrence shall be described. The proportions of AEs and patients with AEs will be compared between the 2 groups. The proportions of patients who used an additional dental consultation for significant post-operative complication or pain will be described and compared, between the PA1704 arm and the BioRoot™ RCS arm, by Pearson's Chi-squared test or Fisher's exact test.

Defects in the devices will be described in the form of a list and proportions will be compared between the 2 groups.

7.7.7. Intermediate analyses:

No interim analysis of the primary criterion is planned. The main analysis will only be carried out after the 2-year follow-up of all patients enrolled.

Two interim analyses of the secondary criteria have been planned. These will be carried out after 6 and 12 months' follow-up for all included patients.

The alpha risk will not be inflated, as the main criterion will not be analyzed in the interim analyses. Therefore, no alpha risk adjustment method is required. The final analysis will focus on the primary and secondary criteria.

For patients treated with the PA1704 ready-to-use filling material and who agree to be followed-up with for up to 5 years, a non-comparative descriptive analysis of secondary performance and safety criteria at 3.5 years and 5 years will be carried out at the end of their participation.

7.7.8. Criteria for stopping the clinical trial from a statistical point of view:

None. Interim analyses are only used to collect data on secondary criteria before the end of the study. The conclusion on the non-inferiority of PA1704 compared to BioRoot™ RCS will only be made on the final analysis at 2 years.

7.7.9. Changes to the statistical analysis plan:

The statistical analysis plan will be drawn up before the first interim analysis is carried out. The initial analysis strategy may undergo minor modifications following each data review, and the new statistical analysis plan will be described in detail at that time.

7.7.10. Specification of sub-groups for further analysis:

The following sub-group analyses will be carried out, at least on the PP population, during the final analysis at 2 years. Other factors not considered in this protocol may be added in the Statistical Analysis Plan.

- For the primary criterion, the rate of effective treatment at 2 years:
 - Prognostic factors at enrolment
 - Presence or absence of a periapical lesion,
 - Indication for endodontic treatment: initial versus repeat endodontic treatment,
 - Factors related to the surgical procedure
 - Type of rinse solution used to finalize root canal disinfection,
 - Operating techniques used: technical platform used (whether or not a microscope was used), manual files versus continuous rotation versus alternative rotation.
- Post-operative pain:
 - Operating techniques used: manual files versus continuous rotation versus alternative rotation.
 - Initial pulp pathology (pre-existing inflammatory situation or necrosis or live pulp),
 - o Preoperative pain (symptomatic tooth at enrolment, preoperative VAS).

7.7.11. Handling missing, unused or erroneous data, including drop-outs and withdrawals:

No imputation method is planned. However, as stated above, patients with treatment failure at 6 or 12 months will be withdrawn from the study and will be considered to have treatment failure at 24 months.

7.7.12. Exclusion of certain information from the hypothesis tests, if relevant:

None.

7.7.13. In the case of multi-center investigations, minimum and maximum number of subjects to be included for each center:

Each center will include 22 to 24 patients with an indication for initial or repeat endodontic treatment. The number of repeat treatments may vary between centers, but will total 30% in the sample. Some investigators, because of their specialty in endodontics, will include a majority of patients with an indication for repeat treatment, whereas GP investigators will probably have more indications for first-line treatment.

8. Data management

Procedures for examining data, cleaning databases, issuing and resolving data queries:

See Chapter 6.6, Data quality and monitoring section.

Procedures for verification, validation and securing of the electronic clinical data systems, where applicable:

The data collected in electronic CRFs is recorded directly in an electronic database using ENNOV software and hosted on a secure health data server in accordance with current regulations. The data collected in the paper logbooks is entered by the CRO into the electronic database using ENNOV software.

Data retention:

See the Archiving section in Chapter 12.4.

9. Amendments to the clinical investigation plan

Requests for substantial modifications will be sent by the CRO, on behalf of the sponsor, to the relevant ethics committees for their opinion and to the competent authorities for authorization, in accordance with law 2004-806 of 9 August 2004 and its implementing decrees in force.

Similarly, non-substantial modifications will be sent for information.

An updated version of the amended protocol must be dated. This new version will be sent to the investigators.

The patient information leaflet should be amended if necessary.

10. Deviations from the clinical investigation plan

The investigator undertakes to comply with this Clinical Investigation Plan (CIP). It is not authorized to deviate from the CIP except in urgent circumstances, in order to protect the rights, safety and health of patients. In this case, deviations may be carried out without the prior agreement of the sponsor, the CRO and the CPP.

Documentation of deviations: each deviation from the protocol must be documented in the CRF or in the data review report.

The investigator must inform SLB Pharma as soon as he/she is aware of any deviation in an eligibility criterion or early study withdrawal.

In order to limit deviations, SLB Pharma will present the CIP in detail to the entire investigating team during the study set-up visit.

11. Counting the devices

Used and unused PA1704 syringes will be counted during site monitoring visits. As a reminder, all used or defective syringes must be stored by the investigator in a collection box provided at the set-up visit (see chapters 2.9 and 0).

At the end of the clinical run, the remaining medical devices will be collected by the CRO for counting before destruction (unused, used or faulty PA1704 syringes, additional equipment, BioRoot™ RCS boxes).

12. Declarations of conformity — Regulatory obligations

